## **Schedule of Assessments:**

Study Day	Screen	1	7	14	21	28	35	42	49	56	84
Event/Assessment					PC		PC		PC		PC
Informed Consent	Х										
Medical History &											
Demographics	X										
Physical Examination	X										
Electrocardiogram	X					X				X	
Vital Signs	X	Х	Х	Х		Х		Х		Х	
Clinical Safety Laboratory											
Tests	X					X				X	
Serum Pregnancy Test	X										
Urine Pregnancy Test		X								X	
Urine Drug Screen	X										
Inclusion/Exclusion Criteria	X										
SCID-I	Х										
Screening neurocognitive	.,										
assessments	X										
Montgomery Asberg Depression Rating Scale		X				x				x	
SLOF		Х								Х	
C-SSRS	Х	Х	Х	Х	Х	Х	Х	Х	Х	Х	Х
AIMS		X				X				X	
Neurocognitive battery		X								X	
CGI-BP		Х				Х				Х	
Young Mania Rating Scale		Х				Х				Х	
Assessment of Concomitant											
Medication	X	X	Х	X	X	X	X	Х	X	X	Х
Assessment of Adverse Events	x	X	X	x	x	x	x	Х	X	х	Х

#### Appendix 2: Prohibited medications:

#### CYP2D6 Inhibitors Moderate to potent CYP2C19 inhibitors

Bupropion Fluconazole
Celecoxib Fluvoxamine
Cinacalcet Ticlopidine
Chloroquine Esomeprazole
Chlorpheniramine Moclobemide
Clemastine Omeprazole
Clomipramine Voriconazole

Diphenhydramine

Duloxetine Atypical Antipsychotics

Fluoxetine Clozapine

Halofantrine
Hydroxyzine
Methadone
Moclobemide
Paroxetine
Pyrilamine
Quinidine
Terbinafine
Tripelennamine
Aripiprazole

#### Major substrates and inhibitors for CYP2D6 [38]

Specific drugs as substrates Inhibitors, drugs

Alprenol Chinidin Amiflamine Fluoxetin

Aprindine Levomepromazine

Atenolol Lobelin
Bufuralol Methadone
Bupranolol Quinidine
Chlorpropamide Trifluperidol

Clomipramine

Codeine Inhibitors, alkaloids

Ajmalicine Debrisoquine Desimipramine Berberine Desmethylcitalopram Coniine Dextromethorphan Ergotamine Dihydrocodeine Gramine Encainide Harmaline Ethylmorphine Sempervirine Flunarizine Vincamine Vinblastine

Fluperlapine Guanoxan Haloperidol Hydrocodone Imipramine Indoramin Maprotiline

Methoxyamphetamine Methoxyphenamine

Metiamide Metoprolol Mexiletine Nortriptyline

Ondansetron Otycodone

Perhexiline

Perphenaxine Phenacetin

Phenformin

Propafenone Propranolol Quinidine

Thioridazine

Timolol

Tomoxetine

Tropisetron

Zuclopenthixol

#### Appendix 3: Emergency protocol:

This procedure will be followed whenever the research staff is in contact with the study participants either in person or via phone

#### **Emergency procedures:**

If there is an apparent imminent medical risk, call 911. A research team member must watch on the subject until Police/Ambulance arrives.

If there is an imminent medical risk, the other immediate safety procedures to be followed by clinical research staff.

If there is no apparent imminent risk, the following protocol will be followed:

- Alert the Principal Investigator (PI) and/or Study Doctor about the problem (provide with demographics and relevant medical information such as suicidal, homicidal ideation/intent, diagnosis, medical condition, etc.)
- Based on the clinical judgment of PI and/or Study Doctor, 911 may be called at any time during this procedure or appropriate care will provided at the site.
- Alert the Research Manager (provide with relevant information)
- Contact the primary treating psychiatrist.
- Pending response (if recommended to proceed to the Emergency Department (ED), discuss the issue with all relevant research staff and participant as well as the participant's family members and/or caregivers if appropriate.
- Call 911
  - In the case of an involuntary hospitalization/ED evaluation call Police a research team member should go with police since "Petition" is required.
  - In the case of a voluntary hospitalization/ED evaluation call Ambulance to escort the patient.
- In the case of suicidal ideation/intent, a research team member must watch on the subject until Police/Security/Ambulance arrives.
- Contact the building security and inform them that Police and/or Ambulance was contacted.
- A Clinical Research Team Member needs to provide documentation from the investigator to give to the police/security regarding the investigator recommendation.
- A Clinical Research Team Member calls ED to alert that patient is on the way and to provide with all necessary information.
- A Clinical Research Team Member follows up with crisis team/on call resident to give information about the patient.

 A Clinical Research Team Member documents all activities for the study file and for correspondence with clinicians/, sponsor, IRB and Janssen Research and Development, LLC.

Data Analysis Plan for Northwestern- Janssen R&D Collaboration Study

Protocol Title: Testing the ability of JNJ-18038683, a selective serotonin (5-HT)7 antagonist, to

improve cognition and reduce residual depressive symptoms in stable bipolar patients

Protocol Identifier Number: 18038683BCD2001

Northwestern University IRB Number: STU00200919-MOD0042

Version: 1.13

Date: 08.04.2021

Goals:

The goals of this study are to evaluate the efficacy of JNJ-18038683 in an 8-week trial to ameliorate the cognitive deficit and reduce residual depressive symptoms in 60 stable bipolar outpatients receiving treatment for depression. JNJ-18038683 will be studied and compared with placebo as adjunctive treatment to standard pharmacologic treatment for bipolar disorder. Sixty patients will be enrolled and randomized with a 1:1 ratio to one dose of JNJ-18038683 or placebo providing 30 subjects for each treatment arm. The initial intention was to follow stratified randomization based on the presence/absence of atypical APDs with 5-HT7 antagonism so that there is a balance in the assignment of active treatment and placebo in individuals who are and are not, receiving atypical APDs with 5-HT7 antagonism. However, due to recruitment difficulties, the stratified randomization method was not able to be followed as anticipated and was amended.

Assessments and Events:

Demographics, medical history, physical examination, serum pregnancy test, urine drug test, SCID-I diagnosis, and screening neurocognitive assessments will be done only during the screening visit. Urine pregnancy testing is performed at the baseline visit.

Table 1: Assessments completed during the screening visit only

Event /Assessment	Screen
Medical History & Demographics	X
Physical Examination	X
Serum Pregnancy Test	X
Urine Drug Screen	X
Inclusion/Exclusion Criteria	X
SCID-I	X
Screening neurocognitive assessments	X

Neurocognitive battery will be the primary measure of interest and evaluated at baseline and 8 weeks. The clinical global severity scores (CGI-BP), Young Mania Rating (YMRS), Scale for Tardive Dyskinesia (AIMS), Montgomery Asberg Depression Rating Scale (MADRS), Electrocardiogram and Clinical Safety Laboratory Tests will be collected at screening or baseline, and at 4 and 8 weeks. A measure of functional ability (SLOF) also will be assessed at baseline and 8 weeks. The schedule of these assessments is listed in table 2.

Table 2: Assessments completed during the screen visits/baseline visits and at week 4 and/or week 8

Event/Assessment	Screen	Day 1*	Day 28	Day 56
Electrocardiogram	Х		X	Х
Clinical Safety Laboratory Tests	Х		X	Х
Montgomery Asberg Depression Rating Scale		Х	Х	Х
SLOF		Х		Х
AIMS		Х	Х	Х
Screening neurocognitive assessment	Х			
Neurocognitive Assessments Cleveland Battery		Х		Х
CGI-BP		Х	Х	Х
Young Mania Rating Scale		Х	Х	Х

^{*}Day 1 is equal to Baseline

Vital signs, C-SSRS (suicide tendency), concomitant medication, and adverse events experienced by patients will be collected during study visits at screening, baseline, and at weeks 1, 2,4, 6, and 8. In addition, data will be collected at weeks 3, 5, 7, and 12 via phone calls for C-SSRS (suicide tendency), concomitant medication, and adverse events.

Table 3: Assessments completed during the screen visits/baseline visits and at weeks 1,2,4,6 and 8

Event/Assessment	Screen	Day 1	Day 7	Day 14	Day 28	Day 42	Day 56
Vital Signs	Х	Х	Х	Х	Х	Х	Х
C-SSRS*	Х	Х	Х	Х	Х	Х	Х
Assessment of Concomitant	Х	Х	Х	Х	Х	Х	Χ
Medication*							
Assessment of Adverse Events*	Х	Х	Х	Х	Х	Х	Х

^{*} assessments will also be collected at 21, 35, 49 and 84 days via phone calls.

Statistical Analysis:

Screening data and drop out data:

Screen assessments listed in table 1 will be summarized for all the patients including reasons for screen failures. Concomitant medications were the reasons for most screen failures and will be documented. Included patients will be compared with excluded patients based on appropriate statistical methods (parametric or non-parametric) for the variables in table 1. During the study period, all dropouts and reasons for drop out will be tabulated.

In this blinded RCT, individuals with bipolar disorder received active drug (JNJ-18038683) or a placebo after screening and the completion of baseline assessments. Subjects in the two treatment arms will be compared on all the baseline efficacy measures, measures of psychopathology related to bipolar disorder, e.g., YMRS, MADRS, CGI-BP, SLOF measures, demographic variables, and suicide status.

Primary analysis for efficacy:

The primary outcome measure for this study is verbal fluency performance as assessed with the Rey Auditory Verbal Learning Test, Rey Verbal Learning Test – Recognition Form, Verbal Fluency Test "Letterforms", and Animal Naming Test. The 8-week evaluation of verbal fluency after randomization is the primary outcome measure. Since the main interest is to measure the treatment effect for verbal fluency improvement from baseline and there is only one follow-up time point for the primary outcome variable, an ANCOVA model will be best suited for this study to compare the treatment effect using baseline value as a covariate. Alternatively, an ANOVA model will be used to compare the percent improvement and changes in the verbal fluency scores across treatment groups. Also, we plan to compare the treatment effect on verbal fluency performance over time using a mixed model. The missing evaluations will be imputed with the last value carried forward method, while model fit statistics will be used to estimate the appropriate covariance structure for this model.

There is both preclinical and clinical evidence that age has an important influence on 5-HT7 receptor function, which is the target of JNJ-18038683. Capacity to respond to JNJ-18038683 may decline with age. Thus, we predict the age of the subject will be related to the extent of improvement in verbal fluency and other measurements in the cognition battery. The relationship of age and percent improvement and the direct change of verbal fluency from baseline to 8 weeks in each treatment arm will be assessed using correlation analysis. The age variable will be used as a continuous variable in the analysis. If the distribution of the age variable is skewed, then age groups will be formed appropriately. In the above described ANCOVA and repeated measures models, age will be use as a covariate to assess the treatment effect. Graphical methods will be used to check for any inflection points of improvement of verbal fluency score in the treatment group compared to placebo. In the treatment group, better improvement is expected in younger patients compared to older patients. This relationship is not expected in placebo-treated patients. Additionally, with the above-mentioned models, the effect of covariates, MADRS total score, YMRS and Clinical Global Severity score on cognition will be examined because baseline mania or depression severity may influence performance on cognitive testing.

Secondary analyses related to efficacy:

The secondary analyses regarding change in verbal fluency test scores will include identification of patients in each arm who improved in verbal fluency scores. The analysis plan includes exploring the effect of concomitant meds, gender or race that might contribute to treatment response. For this purpose, improvement in verbal fluency can be grouped as a dichotomous response and used as a dependent variable in a logistic regression model. The usual method of grouping will be improvement of ≥0.5 SD from the baseline scores. Using this model, the odds of improvement in verbal fluency can be compared in the active treatment group against the placebo group. In this model, the variables, age, gender, lab values and presence/absence of concomitant meds, baseline MADRS total score, YMRS and Clinical Global Severity score mania or depression severity may influence performance on cognitive testing and will be tested as potential covariates using one or few covariates at a time due to sample size restrictions.

Additional secondary analyses will study the effect of treatment group on other cognitive and behavioral measures including: 1) Digital Symbol Task, 2) Brown-Peterson Consonant Trigram Memory Task, 3) WISC-III Mazes; 4) Wisconsin Card Sorting Test; 5) MADRS total score,6) YMRS, and 7) Clinical Global Severity score using a mixed model repeated measure ANCOVA as described above. If indicated, variables such as age, gender, concomitant meds, will be examined, as will be done for the primary outcome measure.

Adverse Events:

A tabular summary of all anticipated and unanticipated serious or non-serious adverse events will be presented, including drop-outs due to any side effects or safety reasons. For each serious or other adverse events, the summary includes the adverse event term, affected organ system, number of participants at risk, and number of participants affected, by the study arm or comparison group. Using appropriate parametric or non-parametric methods, each type of adverse event will be compared between groups. All adverse events, e.g. development of suicidal ideation or behaviors or switch to mania/hypomania, will be examined thoroughly for impact on primary and secondary outcome measures. We will assess group differences, excluding subjects without these two side effects.

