#### 2.2 Rationale for Randomized Controlled Trial of JNJ-18038683 on Cognition and Residual Depressive Symptoms in Bipolar Disorder

Based on the pre-clinical, pro-cognitive effects of 5-HT7 antagonism in our laboratory, along with the reported pre-clinical antidepressant effects of JNJ-18038683, we propose to conduct a randomized, placebo-controlled parallel, design study to assess the effects of JNJ-18038683 on multiple domains of cognition and mood symptoms. Since our preclinical studies show that 5-HT7 receptor blockade is highly effective in improving declarative memory in rodents. the declarative memory measures will be the primary outcome measures. As previously discussed Andressen et. al [39] noted differential functional selectivity of the 5-HT7 receptor, suggesting that the effects of atypical APDs with known 5-HT7 antagonism, such as lurasidone, ziprasidone and risperidone, are modulated via different HTR7 subunits than JNJ1083868. In light of this new information, we proposed to allow some individuals currently prescribed treatment with atypical APDs with 5-HT7 antagonism to be eligible for screening and randomization.

Due to the effect of JNJ-18038683 on depressive symptoms in preclinical paradigms [12], we will investigate the following in the clinical trial the potential antidepressant effect of JNJ-18038683 on patients with baseline MADRS score between 8 and 20.

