# 8.0 Study Endpoints

The declarative verbal memory subscales will be the primary endpoints. Secondary outcome measures will include cognition composite score, the MADRS total score (for those with a MADRS score between 8 and 20 at the time of enrollment) and individual scores for each of the other neuropsychological tests. We will assess JNJ-18038683 effects on functional ability and clinical global severity scores as additional endpoints, as measured by the SLOF and CGI-BP. Further, we will analyze the effect on drug tolerability as determined by the following: body weight, body mass index (BMI), waist circumference, and movement rating scales.

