#### 9.4.2 Cognition battery

The "Cleveland" cognition battery will be administered in this trial, which the PI has used over the past 30+ years as measures of the following cognitive domains: executive functioning, speed of processing, attention/vigilance, working memory, verbal learning, visual learning, reasoning and problem solving

This battery includes the following assessments:

- Wisconsin Card Sorting Test (WCST)
- Digit Symbol Task
- Rey Auditory Verbal Learning Test (Rey-AVLT)
- WISC-III Mazes
- Category Fluency Test
- Verbal Fluency

18

Brown-Peterson Consonant Trigram Memory Task

The cognition battery will be administered at baseline and end of study.

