## 11.0 Data and Specimen Management

#### 11.1 Data Analysis Plan

The primary analysis will be a mixed model repeated measures ANCOVA adjusting for baseline differences in dependent measures, sex and race. Missing data will be imputed by MMRM. We would also examine some variables categorically.

Assumptions for the power analysis included random assignment into one group receiving placebo and one JNJ-18038683. The cognitive battery, as the primary instrument, will be collected at baseline and at end point (8 weeks). Using repeated measure ANCOVA, the time average difference in the response variable will be compared between groups to detect treatment difference. Based on Javitt et al, 2012, we assume the mean baseline verbal learning score will be 36.2, SD 9.4 for both groups. We are assuming the placebo group will show no improvement while the treatment group will improve a mean of 5 points, a medium effect. We assume the correlation coefficient of repeated observation to be 0.5 and the covariance structure to be compound symmetry. The power calculation was conducted with alpha level of 0.05 using one-sided and two-sided tests. Full results are available upon request. With a one sided test, 33 individuals per group are required assuming 5 points improvement of the treatment group compared to the placebo for the desired power of 80% with alpha level of 0.05. We plan to recruit 36 per group to account for drop outs. In the two sided test the sample size per group is 42.

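### The protocol and SAP name three different primary outcomes, and the SAP does not say how the four tests it files under verbal fluency lead to one conclusion

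*SAP*

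**What the plan says.** Protocol section 2.2 argues from the preclinical work that "the declarative memory measures will be the primary outcome measures". Section 8.0 repeats it: "The declarative verbal memory subscales will be the primary endpoints". It then lists among the secondary outcomes "individual scores for each of the other neuropsychological tests". The memory subscales are not named. Section 9.4.2 lists the Rey-AVLT, the "Category Fluency Test" and a verbal fluency test as separate items of the battery, without saying which test serves which domain. The sample size in section 11.1 rests on a single score: "we assume the mean baseline verbal learning score will be 36.2, SD 9.4 for both groups", with a 5-point gain on drug and none on placebo.

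The SAP, under its primary efficacy analysis, says: "The primary outcome measure for this study is verbal fluency performance as assessed with the Rey Auditory Verbal Learning Test". The sentence goes on to add the Rey recognition form, a letter fluency test and an animal naming test. The Week 8 evaluation of this outcome is to be compared by ANCOVA with baseline as covariate. An ANOVA on change and percent improvement is offered as an alternative, and a mixed model is added. In its assessments section, the SAP instead treats the neurocognitive battery as a whole as the main measure of interest.

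**The concern.** There are three competing primary designations: declarative verbal memory, a four-test set called verbal fluency, and the full battery. The SAP explains its departure from stratified randomization but not this one.

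Within the four-test set, the SAP moves between a singular outcome or score and plural scores. One combined score and four separate tests are both possible readings. It names the Rey recognition form, but not which Rey score or trials are analysed. The secondary responder analysis, with its cut at 0.5 SD, rests on the same undefined score.

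Two things are at stake. A result seen only on a fluency test could be reported as the primary finding without answering the memory question that justified and sized the trial. And the error rate and power of the primary test cannot be stated, because there is no rule from which to derive them.

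**Working it through.** **Step 1: the plan's own figure.** Inputs from protocol section 11.1: difference 5, SD 9.4, correlation 0.5, compound symmetry, two time points, alpha 0.05.
- SD of the time average: 9.4 × √((1 + 0.5)/2) = 8.141. The residual SD for the SAP's baseline-adjusted ANCOVA is 9.4 × √(1 − 0.5²) = 8.141, the same.
- 33 per group, one-sided: 5/(8.141 × √(2/33)) = 2.495; Φ(2.495 − 1.645) = 0.8024. The protocol's table gives 0.80235.
- 42 per group, two-sided: 5/(8.141 × √(2/42)) = 2.815; Φ(2.815 − 1.960) = 0.8036.

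The stated sizes are right for one verbal learning score tested once. They say nothing about a four-test outcome.

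**Step 2: false-positive risk under each possible rule.** The documents give no correlations between tests, so 0.3, 0.5 and 0.7 are assumed. Four independent tests at 0.05 would give 1 − 0.95⁴ = 18.5%. Simulated trials (20,000 per case, 30 per arm, baseline-adjusted ANCOVA, two-sided 0.05, no drug effect) gave:

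| Rule | r = 0.3 | r = 0.5 | r = 0.7 |
|---|---|---|---|
| Any one of four significant | 17.6% | 16.1% | 13.7% |
| of which: fluency test(s) only, neither Rey score | 8.0% | 6.7% | 5.0% |
| Either of two Rey scores, unadjusted | 9.6% | 9.4% | 8.8% |
| Two Rey scores with Holm | 5.0% | 4.9% | 4.5% |

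Requiring all four gives under 1% throughout. One equal-weight composite of the four gives 4.9-5.4%.

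**Step 3: power of a composite at 30 per arm, two-sided 0.05.** The effect per test that moves is assumed to be 5/9.4 = 0.532 SD. The mean of k standardised scores with common correlation r has SD √((1 + (k − 1)r)/k). For four tests this is 0.689, 0.791 and 0.880 at r = 0.3, 0.5 and 0.7. For two tests it is √((1 + r)/2) = 0.806, 0.866 and 0.922. Noncentrality = (mean effect ÷ composite SD) ÷ √(0.75 × 2/30), with 57 degrees of freedom. Example, four tests, only the Rey scores moving, r = 0.5: mean effect 0.532/2 = 0.266; 0.266/0.791 = 0.336; 0.336/0.2236 = 1.50; power 32%.

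| Composite and what moves | r = 0.3 | r = 0.5 | r = 0.7 |
|---|---|---|---|
| Four tests; Rey scores only | 40% | 32% | 26% |
| Four tests; fluency moves half as much | 72% | 60% | 51% |
| Four tests; all move equally | 92% | 84% | 76% |
| Two Rey scores; both move | 83% | 77% | 72% |
| Two Rey scores; only one moves | 31% | 27% | 25% |

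With Holm over two Rey scores, if both move, the chance that at least one passes is about 66-73% (simulated on the same inputs).

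**The case against.** The best case for the SAP is that it already points to one outcome and one model. Most of its primary paragraph is in the singular, ANCOVA is called the best-suited model, and the words introducing the ANOVA and the mixed model suggest a ranking. No text says that a win on any single test counts. A four-test composite would hold its error at about 5%. It would also have more power than a Rey composite if the drug helps all four tests, and the documents leave room for that: the protocol background reports preclinical effects on executive function, and the SAP predicts gains in fluency and in other battery measures. The ambiguity also starts in the protocol, whose subscales are plural and unnamed.

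Much of this stands. A reader might infer that the trial carries a 13-18% error rate; that is the worst case under a rule the SAP never states. A reader might also take it as fact that the fluency tests were secondary under the protocol. That is an inference from sections 8.0 and 9.4.2, and so is matching animal naming to the protocol's category fluency test. Nor is a four-test composite always the weaker choice.

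What does not stand is the idea that the singular wording settles the matter. A single outcome built from four tests needs a formula, and none is given. Nor does a change of construct become harmless because the protocol was vague about its subscales: it was clear that the construct was memory.

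**Conclusion.** The point holds and must be fixed. The two documents disagree on the primary construct, the SAP itself gives two designations, and no rule turns four test results into one conclusion. The possible rules span a false-positive risk from under 1% to about 18%, and a four-test composite spans 26% to 92% power depending on which tests respond. These figures rest on assumed inter-test correlations of 0.3 to 0.7, equal weights, the protocol's 0.5 baseline correlation for every score, an assumed 0.53 SD effect, and all 30 per arm evaluable.

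A reader might infer that the outcome was switched after results were seen. The documents do not support that. The SAP describes treatment in the past tense, but nothing in it shows that the blind was broken; it only makes the timing of any amendment important.

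The shortfall from the protocol's 33, 36 or 42 per group to 30 per arm, power at a smaller number evaluable, and the difference in covariates (sex and race in the protocol, age in the SAP) are separate issues and are not part of this point.

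**What to change.** Issue a dated SAP amendment before unblinding, with the reason stated.

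1. Reconcile protocol sections 2.2 and 8.0 with the SAP's assessments and primary-analysis sections, and define one Week 8 primary test. The default that fits the protocol's rationale and sizing is one named Rey-AVLT score (stating which trials) or one defined Rey composite. The alternative is to keep both Rey measures and use Holm across the two. Move letter fluency and animal naming to secondary, and stop labelling Rey results as verbal fluency. If the sponsor prefers a four-test composite, it should give the formula, justify it and amend the protocol endpoint to match.
2. State that the baseline-adjusted ANCOVA is the single primary analysis, that the change, percent-change and mixed-model analyses are supportive, and what alpha and sidedness apply.
3. If the blind is already broken, label the choice of primary score post hoc.

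The cost is SAP wording and a matching change or note in the protocol; no new data are needed. The downside under the default is that a result on fluency alone can no longer be claimed as the primary finding.

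### The SAP's percent-improvement analyses lose power against its own ANCOVA and show a spurious gain within each arm, so they should be deleted or kept descriptive

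*SAP*

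**What the plan says.** The SAP, under Primary analysis for efficacy, calls an ANCOVA on the 8-week value with baseline as covariate best suited. The next sentence reads "Alternatively, an ANOVA model will be used to compare the percent improvement and changes in the verbal fluency scores across treatment groups". The SAP does not label this ANOVA a sensitivity or descriptive analysis, and it gives no rule for when it replaces the ANCOVA. It gives no reason for the percent scale and does not say how low baseline scores are handled.

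The age paragraph under the same heading uses the metric again, by correlation: "The relationship of age and percent improvement and the direct change of verbal fluency from baseline to 8 weeks in each treatment arm". The SAP expects younger patients to gain more on active drug and expects no such relation on placebo. It also plans to include age as a covariate in the ANCOVA and repeated-measures models.

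Protocol section 11.1 plans a baseline-adjusted analysis and does not mention percent change. Its sample-size paragraph states the planning values: "we assume the mean baseline verbal learning score will be 36.2, SD 9.4 for both groups". The same paragraph sets the gain at 5 points on active drug and zero on placebo, with a between-visit correlation of 0.5 under compound symmetry.

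**The concern.** Percent improvement divides each patient's change by that patient's own baseline score, which is measured with error. A patient who scores low at baseline partly by chance tends to score higher next time, and the small denominator magnifies that gain. A patient who scores high by chance tends to fall back, but over a larger denominator. The two do not offset, so the average percent change is positive even when nobody has changed. The division also adds variance, and the planned ANOVA has no baseline covariate to remove any of it.

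Two things are at stake. If the ANOVA on percent improvement carries weight in the efficacy conclusion, a real effect is more likely to be missed in a trial of 30 per arm. The protocol's own calculation asks for 33 per group one-sided or 42 two-sided. Separately, any percentage quoted for a single arm would suggest improvement that did not occur.

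**Working it through.** **Inputs.** Protocol 11.1: mean 36.2, SD 9.4, correlation 0.5, effect 5 points on active and 0 on placebo, alpha 0.05 one-sided and two-sided. SAP, Goals: 30 per arm. The lowest plausible baseline score is not in the documents. It is an assumption (10 to 12 in the main runs, varied from 1 to 20).

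**The protocol's own figure.** For a time-averaged difference over two visits, SD = 9.4 × √((1 + 0.5)/2) = 8.14. Then n = 2 × ((z_α + 0.842) × 8.14/5)².
- One-sided, z = 1.645: 32.8, so 33 per group, power 0.802. This matches "With a one sided test, 33 individuals per group are required assuming 5 points improvement of the treatment group compared to the placebo".
- Two-sided, z = 1.960: 41.6, so 42. This matches "In the two sided test the sample size per group is 42".

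The inputs are therefore being read as the protocol meant them.

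**ANCOVA and raw change at 30 per arm, normal approximation, two-sided.**
- ANCOVA: residual SD = 9.4 × √(1 − 0.5²) = 8.14; SE = 8.14 × √(2/30) = 2.10; 5/2.10 = 2.38; 2.38 − 1.96 = 0.42; power about 66%.
- Raw change: SD = 9.4 × √(2 × (1 − 0.5)) = 9.4; SE = 9.4 × √(2/30) = 2.43; 5/2.43 = 2.06; 2.06 − 1.96 = 0.10; power about 54%.

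**Simulation for percent change** (bivariate normal scores, 10,000 to 40,000 trials per setting, t-distribution critical values):

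| Analysis | Power, one-sided | Power, two-sided |
|---|---|---|
| ANCOVA on Week 8 score | 75% | 64% |
| ANOVA on raw change | 66% | 53% |
| ANOVA on percent change | 56–57% | 43–44% |
| Percent change with baseline as covariate | – | 56–57% |

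**Splitting the two-sided loss.** ANCOVA to raw change is 64 − 53 = 11 points, the price of dropping the covariate. Raw to percent change is 53 − 43 = 10 points, the price of the division. With the covariate kept in both models, the metric alone costs 64 − 57 = 7 points. The division therefore accounts for about 7 to 10 points of about 20.

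**Sensitivity of the total loss.**
- Correlation 0.3: 24 points. Correlation 0.7: 12 to 16. Correlation 0.8: 7 to 10.
- Baseline floor of 20: 13 to 14.
- Effect proportional to baseline, correlation 0.5: 18 to 22.
- Lognormal scores, correlation 0.5: 10 to 11. Here raw and percent change both have about 53% power, so the whole loss is the missing covariate.
- Lognormal scores, correlation 0.8, additive effect: 91.6% against 90.8%, under 1 point.

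ANCOVA had the higher power in every setting tried.

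**False gain with no true change.** CV = 9.4/36.2 = 0.26. Expected mean percent change is approximately (1 − 0.5) × 0.26² = 3.4%. Simulation gives about +4% (range +1.6% to +4.5% for floors from 20 down to 1), while the mean raw change and median percent change are close to 0 in the main runs. The gain arises in both arms. Type I error of the between-arm percent test is 5.1% two-sided and 5.2% one-sided.

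**Age.** Assume a correlation r between age and score that is equal at both visits, and a constant 5-point effect. At r = −0.3 the spurious correlation of age with percent improvement is about +0.06. The standard error of a correlation in 30 patients is about 1/√27 = 0.19. Relating age to the baseline-adjusted Week 8 score within an arm is worse. The partial correlation is (r − 0.5r)/√((1 − r²)(1 − 0.25)), which at r = −0.3 is −0.15/0.826 = −0.18. At r = −0.1 it is −0.05/0.862 = −0.06, and at r = −0.5 it is −0.25/0.75 = −0.33. That bias lies in the direction the SAP predicts. It is the same in both arms, so a treatment-by-age contrast removes it.

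**The case against.** The best defence is that the SAP already prefers ANCOVA and introduces percent improvement only as an alternative, next to raw change. Power falls only if percent improvement decides the conclusion. That stands, and it limits the point: the trial does not have 43% power merely because this ANOVA is listed. But the ANOVA sits under the primary heading with no supportive label and no rule for its use, and percent improvement appears again in the age analysis.

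A reader might infer more than the documents support in three ways.
- *That the percent metric costs 20 points.* About half of that gap is the missing covariate, which the raw-change ANOVA loses too.
- *That the +4% gain can produce a false treatment effect.* It cannot. The gain is common to both arms, the planned ANOVA compares arms, and the type I error stays at about 5%.
- *That percent improvement seriously distorts the age hypothesis.* The age norms in Protocol section 3.1, criterion 16, apply to the screening tests and say nothing about raw baselines on the outcome tests. The −0.3 correlation is an assumption, the resulting artefact of about +0.06 is small against a standard error of 0.19, and the SAP correlates age with direct change as well.

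Percent change might be thought natural if the drug effect scaled with baseline. That does not rescue it: with a proportional effect and correlation 0.5, the loss against ANCOVA is still 18 to 22 points.

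**Conclusion.** The point holds in a limited form. On the protocol's planning inputs, an ANOVA on percent improvement has about 43% two-sided power at 30 per arm, against about 64% for the ANCOVA. Some 7 to 10 points of that difference are due to the division by baseline. It also shows a mean gain of about 4% in an arm where nothing changed. The harm is confined to lost power, if the analysis is given weight, and to within-arm percentages. The between-arm test remains valid.

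The size rests on a correlation of 0.5, roughly normal scores and some low baselines. It shrinks with a higher correlation or skewed scores and nearly disappears when both apply. The planning figures describe a verbal learning score. The SAP's primary outcome also includes recognition, letter fluency and animal naming, for which the documents give no mean or SD, so the loss on those measures is unknown. Because the ANCOVA stays in the plan, this does not invalidate the trial, but it is worth correcting.

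**What to change.** Delete percent improvement from the ANOVA and from the age correlations, or state that it is descriptive and carries no test. Base the efficacy conclusion on the baseline-adjusted Week 8 difference in score points with its confidence interval. If a percentage is wanted for readers, express that adjusted difference as a percentage of the pooled baseline mean.

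Assess the age hypothesis by adding a treatment-by-age term to the baseline-adjusted ANCOVA and reporting it with a confidence interval. This matches the SAP's own prediction, which contrasts the two arms. Do not replace the correlations by relating age to the baseline-adjusted score within each arm, for the reason shown in the working.

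The cost is a short change to the SAP wording and somewhat less programming. What is lost is an intuitive percentage for each patient. The interaction will be estimated imprecisely with 60 patients and should be presented as such.
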